3. OBJECTIVES

3.1. Primary objective

- To assess the persistence of humoral antibodies up to 3 years after the last planned visit (Month 14) in the NTHi-Mcat-001 study.

3.2. Secondary objective

- To assess the safety of the investigational NTHi-Mcat vaccine in terms of serious adverse events (SAE) and potential immune-mediated diseases (pIMD) up to 3 years after the last planned visit (Month 14) in the NTHi-Mcat-001 study.

4. ENDPOINTS

4.1. Primary endpoint

- Humoral immune response to the components of the NTHi Mcat investigational vaccine formulations at Month 20, Month 26, Month 32, Month 38, Month 44 and Month 50 in all subjects:
 - Anti-PD, anti-PE, anti-PilA and anti-UspA2 antibody concentrations.

4.2. Secondary endpoints

- Occurrence of any SAE, during the entire study period in all subjects.
- Occurrence of any pIMD during the entire study period in all subjects.

CONFIDENTIAL204913 (NTHI-MCAT-006 EXT:001)
Statistical Analysis Plan Final

5. ANALYSIS SETS

5.1. Definition

Note that in order to align to ICH and CDISC terminology the Total Vaccinated Cohort and the According To Protocol cohort have been renamed Exposed Set (ES) and Per-Protocol Set (PPS) respectively.

5.1.1. Exposed Set

The ES for safety analysis will include all subjects from STEP 2 of NTHI-Mcat-001 (201281) enrolled in this follow-up study.

The ES for immunogenicity analysis will include all subjects from STEP 2 of NTHI-Mcat-001 (201281) enrolled in this follow-up study and for whom immunogenicity data are available.

5.1.2. Per-protocol Set

The PPS will consist of all subjects from the ES who will comply with eligibility criteria, study procedures up to the last subject last visit and had immunogenicity results in the epoch.

More specifically, the PPS will include all eligible subjects:

- Who met all eligibility criteria.
- Who did not receive a concomitant medication/ product/vaccine leading to the elimination from the Per Protocol analysis.
- Who did not present with an intercurrent medical condition leading to elimination from the Per Protocol analysis.
- Who complied with at least one of the immunogenicity blood sample timings.
- For whom immunogenicity results are available for at least one assay in at least one of the follow-up time points.

5.2. Criteria for eliminating data from Analysis Sets

Elimination codes are used to identify subjects to be eliminated from analysis. Detail is provided below for each set.

5.2.1. Elimination from Exposed Set

Code 900 (invalid informed consent or fraud data) will be used for identifying subjects eliminated from ES.

CONFIDENTIAL204913 (NTHI-MCAT-006 EXT:001)
Statistical Analysis Plan Final**5.2.2. Elimination from Per-protocol analysis Set****5.2.2.1. Excluded subjects**

A subject will be excluded from the PPS analysis under the following conditions

Table 1 Elimination Codes¹

Code	Condition under which the code is used
900	Invalid informed consent or fraud data
1040	Administration of concomitant vaccine forbidden in the protocol: any investigational or non-registered vaccine used during the study period.
2010	
Protocol violation (inclusion/exclusion criteria)
 
Inclusion:
 
 Subjects who previously participated in STEP 2 of study NTHi-Mcat-001 (201281), and performed the last study visit (Month 14) and received the 2 study vaccinations. Subjects who, in the opinion of the investigator, can and will comply with the requirements of the protocol (e.g. return for follow-up visits). And subjects' Legally Acceptable Representative(s) [LAR(s)] who, in the opinion of the investigator, can and will comply, with the requirements of the protocol. Written informed consent obtained from the subject/ LAR(s) of the subject prior to performance of any study specific procedure. 
Exclusion:
 
 Use of any investigational or non-registered product (drug or vaccine) during the period starting 30 days before the first follow-up study visit (Month 19 to Month 20), or planned use during the study period. Chronic administration (defined as more than 14 days in total) of immunosuppressants or other immune-modifying drugs since the end of the NTHi-Mcat-001 study. For corticosteroids, this will mean prednisone \geq 20 mg/day, or equivalent. Inhaled and topical steroids are allowed. Administration of long-acting immune-modifying drugs at any time during the study period (e.g. infliximab). Concurrently participating in another clinical study, at any time during the study period, in which the subject has been or will be exposed to an investigational or a non-investigational vaccine/product (pharmaceutical product or device). Administration of immunoglobulins and/or any blood products during the period starting 3 months before the first follow-up visit or planned administration during the study period. Current alcoholism and/or drug abuse. Has significant disease (including significant neurological or psychological disorders), in the opinion of the investigator, likely to interfere with the study and/or likely to cause death within the study duration.

¹ These will be identified during review of individual data listings

CONFIDENTIAL

204913 (NTHI-MCAT-006 EXT:001)

Statistical Analysis Plan Final

Code	Condition under which the code is used
	
 Any other condition that the investigator judges may interfere with study findings.
2040	
Administration of any medication forbidden by the protocol:
 
 Any investigational or non-registered drug used during the study period. Immunosuppressants or other immune-modifying drugs administered chronically (i.e. more than 14 days in total) during the study period. For corticosteroids, this will mean prednisone \geq 20 mg/day (for adult subjects), or equivalent. Inhaled and topical steroids are allowed. Long-acting immune-modifying drugs administered at any time during the study period (e.g. infliximab). Immunoglobulins and/or any blood products administered during the study period.
2050	Underlying medical condition forbidden by the protocol: if, during the study, subjects incur a condition that has the capability of altering their immune response (i.e. confirmed immunosuppressive or immunodeficient condition, including HIV).
2060	Concomitant infection related to the vaccine which may influence immune response: infection related to any of the vaccine component.
2070	Concomitant infection not related to the vaccine which may influence immune response.
2090	Blood Sample taken but: non compliance with blood sampling schedules (dates of BS not corresponding to adapted protocol intervals or unknown BS dates: -20/+20 days).
2100	Serological results not available for antigens POST vaccination (including lost samples, blood sample not done, unable to test, absence of parallelism). If results for all antigens are missing or unknown.
2110	Essential serological results temporarily missing because not tested yet (For interim analysis).
2120	Obvious incoherence, abnormal serology evolution or error in data (incoherence between CRF and results, wrong sample labelling).
2130	Subject not planned to be bled for their all blood sampling visits
2140	Temperature deviation from range defined in protocol and/or SPM and/or Lab Manual.

5.3. Important protocol deviation not leading to elimination from per-protocol cohort

The following important protocol deviations will be reported by groups:

- Short follow-up: subjects who completed the last study contact before the minimum length of follow-up requirement.
- In case of immunogenicity sub-set for different blood samples schedules, the subjects who follow an erroneous bleeding schedule could be mentioned.

CONFIDENTIAL204913 (NTHI-MCAT-006 EXT:001)
Statistical Analysis Plan Final

6. STATISTICAL ANALYSES

Note that standard data derivation rule and statistical methods are described in annex 1 and will not be repeated below.

6.1. Demography

6.1.1. Analysis of demographics/baseline characteristics planned in the protocol

Demographic characteristics (retrieved from parent study Nthi-Mcat-001) age at the first dose in years, gender, ethnicity, race, smoking/exposure history status, pulmonary function test baseline results, height, weight and a cohort description will be summarized by group using descriptive statistics:

- Frequency tables will be generated for categorical variables such as race;
- Mean, median and standard deviation will be provided for continuous data such as age.
- The distribution of subjects enrolled among the study sites will be tabulated as a whole and per group.
- Withdrawal status will be summarised by group using descriptive statistics:
 - The numbers of withdrawn subjects will be tabulated according to the reason for withdrawal.
- The number of subjects enrolled into the study as well as the number of subjects excluded from different population of analysis will be tabulated.

6.2. Immunogenicity

6.2.1. Analysis of immunogenicity planned in the protocol

The primary analysis will be based on the Per Protocol Set. If, in any study group, the percentage of enrolled subjects with serological results excluded from the Per Protocol Set for analysis of immunogenicity is 10% or more, a second analysis based on the Exposed Set for immunogenicity will be performed to complement the Per Protocol Analysis.

Within group assessment

For each group, at Visit 1 (Month 20), Visit 2 (Month 26), Visit 3 (Month 32), Visit 4 (Month 38), Visit 5 (Month 44) and Visit 6 (Month 50), when blood samples are available for humoral immune response and for each assay:

CONFIDENTIAL

204913 (NTHI-MCAT-006 EXT:001)
Statistical Analysis Plan Final

- Seropositivity rate and their exact 95% CI will be tabulated.
- Adjusted geometric mean concentrations (GMCs) and associated two-sided 95% confidence intervals (CIs) will be computed. These will be obtained from one-way ANCOVA with group as fixed effect and Visit 1 (Day 0) concentration in NTHi-Mcat-001 as regressor.
- Geometric Mean Ratios (GMRs) with respect to Visit 1 (Day 0) in NTHi-Mcat-001 will be calculated for Visit 1 (Month 20), Visit 2 (Month 26), Visit 3 (Month 32), Visit 4 (Month 38), Visit 5 (Month 44) and Visit 6 (Month 50), for each group.
- A graph of the GMCs across the time (Visit 1 (Month 20) to Visit 6 (Month 50)) will be considered. Measures such as the maximum concentration, the time of the peak of concentration will be computed. One graph per strain will be created. Each graph will show the 3 groups.
- For each strain, antibody concentrations distribution will be investigated using Reverse Cumulative Curves.
- Subject graphs of immunogenicity results over time will be provided.

These analyses will also be performed for each level of the following minimisation factor: age (50-59 years vs. 60-71 years).

Between group assessment

Comparative analyses will be exploratory with the aim to characterise the difference between the 10-10-10-AS and 10-10-3-AS groups in humoral immune response.

At each visit, differences in percentages and two-sided 95% CIs between the groups 10-10-10-AS versus 10-10-3-AS, will be calculated and the associated confidence interval for the difference will be constructed using the standardised asymptotic method.

At each visit, the difference in terms of GMCs will be evaluated, by computing the 95% CIs of the GMC ratios between 10-10-AS and 10-10-3-AS groups, using a one-way ANCOVA model on the logarithm10 transformation of the concentrations. The ANCOVA model will include the group category as fixed effects and the Visit 1 (Day 0) concentration in NTHi-Mcat-001 study as regressor.

These differences should be interpreted with caution, considering that there will be no adjustment for multiplicity of endpoints.

Comparison with placebo

Placebo comparative analyses are planned to evaluate the prematurely stopping of the trial.

GMCs and GMC ratios, together with 95% CIs will be computed, at each visit, using a one-way ANCOVA model on the logarithm 10 transformation of the concentrations. The ANCOVA model will include the group category as fixed effects and the Visit 1 (at Day 0) concentration in NTHi-Mcat-001 study as regressor. The GMC ratios (vaccinated

CONFIDENTIAL

204913 (NTHI-MCAT-006 EXT:001)

Statistical Analysis Plan Final

versus placebo) point estimates obtained from ANCOVA model will be considered for the evaluation of stopping the trial.

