#### **4.2. Inclusion criteria for enrolment**

Deviations from inclusion criteria are not allowed because they can potentially jeopardize the scientific integrity, regulatory acceptability of the study or subject safety. Therefore, adherence to the criteria as specified in the protocol is essential.

All subjects must satisfy ALL the following criteria at study entry:

- Subjects who previously participated in STEP 2 of study NTHI-Mcat-001 (201281), and performed the last study visit (Month 14) and received the 2 study vaccinations.
- Subjects who, in the opinion of the investigator, can and will comply with the requirements of the protocol (e.g. return for follow-up visits). And subjects' Legally Acceptable Representative(s) [LAR(s)] who, in the opinion of the investigator, can and will comply, with the requirements of the protocol.
- Written informed consent obtained from the subject/ LAR(s) of the subject prior to performance of any study specific procedure.

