### 5.6.3. Collect demographic data

Record subject number from parent trial and demographic data such as year of birth, sex, race and ethnicity in the subject's eCRF.

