### 10.6.1. Humoral immune response

#### Within groups evaluation

For each group, at each time point when blood samples are collected for humoral immune response and for each assay:

- Seropositivity rate and the exact 95% CI will be tabulated.
- GMCs and their 95% CI will be calculated.
- Antibody concentrations distribution will be investigated using Reverse Cumulative Curves.
- Subject graphs of immunogenicity results over time will be provided.

**CONFIDENTIAL**204913 (NTHI-MCAT-006 EXT:001)  
Protocol Amendment 1 Final**Between groups evaluation**

Comparative analyses will be exploratory with the aim to characterise the difference between the 10-10-10-AS and 10-10-3-AS groups in humoral immune response.

The difference in terms of GMCs will be evaluated by computing the 95% CIs of the GMC ratio between groups by using a one-way *ANCOVA* model on the logarithm10 transformation of the concentrations/ titres. The *ANCOVA* model will include the group category as fixed effects and the pre-Dose 1 concentration in NTHi-Mcat-001 study as regressor. The groups will be considered significantly different if the 95% CI for the GMC ratio between the two groups does not contain the value 1. **(Amended 28 June 2018)**

However, these differences should be interpreted with caution, considering that there will be no adjustment for multiplicity of endpoints.

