8.2. Statistical considerations for interim analyses

Three interim analyses will be performed on all data obtained up to Month 20, Month 26 and Month 38, respectively. The study may be stopped if the GMC ratio (point estimate; Active [10-10-10-AS and 10-10-3-AS groups] versus PLACE2) for at least 2 out of 4 antigens is ≤ 2 , conclusion of further blood draws and early stop of the trial may be considered. Therefore, 2 GMC ratios per antigen will be calculated: 10-10-10-AS versus PLACE2, and 10-10-3-AS versus PLACE2.

- The analysis of data up to Visit 1 (Month 20) will be performed in a first step for Interim 1. This analysis will include:
 - The analysis of primary objective, as described in the section [6](#) of this document, based on the analysis of humoral immunogenicity results up to six months (Month 20) following last study visit in NTHI-Mcat-001.
 - The analysis of secondary objective, as described in the section [6](#) of this document, based on safety data collected between last visit in parent study NTHI-Mcat-001 (Month 14) and up to Visit 1 (Month 20).

This analysis will be performed on cleaned data and will be reviewed internally only. Individual listing will be provided at this stage.

If the data of the NTHI-MCAT 001 study will not be available and cleaned (freezed), an ANOVA model with only group as independent variable will be fitted instead of the planned ANCOVA model to estimate GMR between groups and placebo.

CONFIDENTIAL204913 (NTHI-MCAT-006 EXT:001)
Statistical Analysis Plan Final

- The analysis of data up to Visit 2 (Month 26) will be performed in a second step for Interim 2. This analysis will include:
 - The analysis of primary objective, as described in the section [6](#) of this document, based on the analysis of humoral immunogenicity results up to one year (Month 26) following last study visit in NTHi-Mcat-001 study.
 - The analysis of secondary objective, as described in the section [6](#) of this document, based on safety data collected between last visit in parent study NTHi-Mcat-001 (Month 14) and up to Visit 2 (Month 26).

This analysis will be performed on cleaned data and will be reviewed internally only. Individual listing will be provided at this stage.

- The analysis of data up to Visit 4 (Month 38) will be performed in a third step for Interim 3. This analysis will include:

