11.2.2. Demography

- Age: Age at the first dose in parent study, computed as the number of units between the date of birth and date of the first dose in parent study. Note that due to incomplete date, the derived age may be incorrect by 1 month when month is missing from the birthdate. This may lead to apparent inconsistency between the derived age and the eligibility criteria/the age category used for randomization.

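### Between-group and placebo ANCOVAs leave out age category, a parent-study minimisation factor; the GMC-ratio intervals are modestly wider than needed if age predicts antibody level (minor)

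*SAP*

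**What the plan says.** - **Between-group model.** For 10-10-10-AS versus 10-10-3-AS, SAP 6.2.1 states: "The ANCOVA model will include the group category as fixed effects and the Visit 1 (Day 0) concentration in NTHi-Mcat-001 study as regressor".
- **Placebo comparison.** The same section again uses group and "the Visit 1 (at Day 0) concentration in NTHi-Mcat-001 study as regressor".
- **Protocol.** Section 10.6.1 gives the same model for both comparisons: "the group category as fixed effects and the pre-Dose 1 concentration in NTHi-Mcat-001 study as regressor".
- **Interim 1 fallback.** If parent-study data are not yet available and cleaned, SAP 8.2 says "an ANOVA model with only group as independent variable will be fitted instead of the planned ANCOVA model".
- **Age.** The within-group part of SAP 6.2.1 ends with "These analyses will also be performed for each level of the following minimisation factor: age (50-59 years vs. 60-71 years". SAP 11.2.2 mentions a possible "apparent inconsistency between the derived age and the eligibility criteria/the age category used for randomization".

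Nothing is randomised in this study (protocol 5.3), so the age factor must come from allocation in NTHi-Mcat-001. That is an inference, but a direct one.

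**The concern.** A factor used to balance allocation normally belongs in the comparison model. If it is balanced and prognostic but left out, its variance stays in the residual, and the intervals are too wide and over-cover.

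Balance may also not last. This study enrols only subjects who "performed the last study visit (Month 14) and received the 2 study vaccinations" and who agree to return. If the age mix of the groups has drifted apart, an unadjusted ratio also carries the age difference.

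The by-age repeats do not deal with either case. They come before the between-group heading and give summaries within each stratum, not an age-adjusted ratio.

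Little rides on this. Protocol 10.8 and SAP 7 make the analyses descriptive, and the stopping rule reads the point estimate of the ratio against 2, not its interval. The interval's one formal use is the protocol 10.6.1 label of significant difference when the 95% CI excludes 1.

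**Working it through.** The plan states no sample size, CI width, age effect, SD or age split, so there is no figure to reproduce.

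**Inputs.** From the documents: three groups of up to 30 (N = 90), two-sided 95% CIs, and model terms group plus Day 0. Assumed: a 50/50 age split, and R2 (the share of variance left after group and Day 0 that age explains) of 0, 5, 10 or 20%. Residual degrees of freedom are 86 without age and 85 with it; t(0.975) is 1.9879 and 1.9883.

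**Change in log-scale CI width from adding age**

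- *A, age exactly balanced.* Without age the residual mean square is proportional to (1−R2) + R2·90/86; with age, to (1−R2). Width ratio = sqrt[(1−R2) / ((1−R2) + R2·90/86)] × 1.9883/1.9879.
- *B, balanced in the parent study, 25 of 30 per group return at random.* Simulation only.
- *C, balance lost (age random across groups).* Width ratio = sqrt[(1−R2)·86/85] × 1.9883/1.9879. At R2 = 5%: 0.9747 × 1.0060 = 0.981.

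| R2 | A formula | A simulated | B simulated | C formula and simulated |
|---|---|---|---|---|
| 0% | 0.0% | 0.0% | +0.1% | +0.6% |
| 5% | −2.6% | −2.5% | −2.5% | −1.9% |
| 10% | −5.3% | −5.2% | −5.0% | −4.6% |
| 20% | −11.0% | −10.9% | −10.9% | −10.0% |

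The simulations used 4,000 runs per setting and a Day 0 correlation of 0.5. With 60 subjects, C gives at most +1.0, then about −1.7, −4.2 and −9.7%. For the Interim 1 ANOVA (N = 90) the changes are 0.0, −2.6, −5.2, −10.9% if balanced and +0.6, −2.0, −4.6, −10.0% if random.

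**Coverage without age.** In A it is 95.0, 95.6, 96.1 and 97.2% by formula. In B it is about 95, 95, 96 and 97%. In C it stays near 95% with or without age.

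**Break-even in C.** Adding age narrows the interval once R2 exceeds 1 − 1/1.0060², which is 1.2% (1.9% with 60 subjects). In A the break-even is about 0.

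**On the ratio scale.** At an assumed residual log10 SD of 0.4, the CI factor without age is 10^(1.988 × 0.4 × sqrt(2/30)) = 10^0.2053 = 1.60. Under C it becomes 1.59, 1.57 and 1.53 at R2 of 5, 10 and 20%.

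**Age effect needed.** With a 50/50 split the fold difference between age levels is 10^(2·sqrt(R2)·SD). For SD 0.3-0.5 that is 1.4-1.7, 1.5-2.1 and 1.9-2.8-fold at R2 of 5, 10 and 20%.

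**Age acting only on the vaccine response.** If age explains r of the variance among vaccinees and none in placebo, the share in a three-group model is (4/9)r / [(1−r) + (2/3)r]. For r = 5, 10, 20% this is 2.3, 4.6 and 9.5%. The simulated gain under A falls to 1.2, 2.4 and 5.0%.

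**Point estimate.** A difference d between groups in the share aged 60-71 shifts the unadjusted ratio by 10^(d × delta), where delta is the age effect in log10. For d = 0.10 and delta = 0.1-0.3 the factor is 1.02-1.07. The SD of d is sqrt(2 × 0.25/30) = 0.129 in C and 0.059 in B. A 1.96 SD chance imbalance therefore shifts the ratio by 1.06-1.19 in C and 1.03-1.08 in B.

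**The case against.** The case for leaving the model alone is reasonable. Protocol and SAP agree on it, and it is valid: coverage without age is about 95% or higher in every scenario. The comparisons are descriptive, stopping is optional, and SAP 6.2.1 does not repeat the significance label. The gain depends on an age effect that the documents do not give. An R2 of 20% needs about a two- to three-fold residual difference between age levels, and an effect confined to vaccinees halves the gain. Where balance is lost and R2 is below 1-2%, adding age widens the interval slightly. The parent allocation algorithm is not in these documents. Age is not ignored either: the within-group results are repeated by age level, and SAP 6.1.1 summarises age by group, so an imbalance would be visible.

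All of this stands, and it limits the point to minor. It does not remove it. No planned analysis gives an age-adjusted ratio, and showing an imbalance does not correct for it. The possible loss is at most about 1% of width, while a moderate age effect returns several times that. Protocol 1.1.3 itself describes weakened responses and impaired long-term immune memory in the often elderly target population. That makes an age effect plausible but says nothing about its size.

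**Conclusion.** The concern holds, as a minor point. Age category is absent from both GMC-ratio models in both documents and from the Interim 1 fallback. At R2 of 5-10% the CIs are about 2-5% wider than needed, a small gain in absolute terms. If age has no effect beyond group and Day 0, nothing is gained. The bias in the ratio from age imbalance is also small, though it feeds the point estimate that the stopping rule compares with 2. The direction follows from standard theory; the size rests on the assumed R2, SD and age split. None of this applies to the within-group adjusted GMCs, for which no over-coverage is claimed.

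**What to change.** In SAP 6.2.1 (between-group and placebo parts) and protocol 10.6.1, replace the model sentence with: *Fixed effects are group and age category (50-59, 60-71 years, as applied at allocation in NTHi-Mcat-001); the regressor is the log10 Day 0 concentration from NTHi-Mcat-001.* Stating log10 for the regressor is only a clarification. Keep the separate model per visit.

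In SAP 8.2 make the fallback an ANOVA with group and age category. If the allocation category is not available at Interim 1, derive it from the "demographic data such as year of birth, sex, race and ethnicity" collected at Visit 1 (protocol 5.6.3), and state that subjects near 59/60 may be misclassified.

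If adjusted GMCs come from the same model, add: *Age levels are weighted by their observed proportions in the analysis set.* This matters because equal weights would shift adjusted GMCs by 10^((0.5 − p) × delta), where p is the share in the smaller age level. For an assumed p of 0.35-0.40 and delta of 0.1-0.3 that is a factor of 1.02-1.11. The age term drops out of the tables by age level.

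The cost is a sentence in each place and one degree of freedom. If age has no effect, the CI is 0-0.6% wider with 90 subjects and at most 1.0% wider with 60.
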